3.6. Subject Replacement

There will be no replacement.

4. TRIAL SCHEDULE

Part of research Schedule:

Patients who meet the inclusion criteria will be invited to participate in this study. Patient will be randomly assigned to either phacoemulsification alone, or phacoemulsification with iStent by random envelope shuffle technique.

After operation the patient will be followed up at day 1, week 1, week 2, months 1, 3, 6 and 12.

At each visit the patient will have the following tests: Tonometry (IOP check) - Not to be taken by the operating surgeon, to be taken by 2 people, one IOP checker and one reader.

Part of Standard of Care:

At each visit:

Visual Acuity, Slit lamp examination and Fundoscopy.

At 6 monthly intervals:

Visual field examination

5. STUDY DESIGN

Single centre, randomised prospective trial, the patient and the IOP checking staff will be blinded. Randomised by random envelope shuffle technique.

1:1 ratio allocation

2 arms: phacoemulsification alone and phacoemulsification and iStent.

16 patients in each arm, 32 patients in total.

The post-operative management is the same for both arms

After operation the patient will be followed up at day 1, week 1, week 2, months 1, 3, 6 and 12.

At each visit the patient will have the following tests: Tonometry (IOP check) - Not to be taken by the operating surgeon, to be taken by 2 people, one IOP checker and one reader.

The target IOP is 18mmHg for patients with PAC or mild PACG. If the IOP rises above 18mmHg in 2 consecutive visits then the original glaucoma medication(s) will be reinstated or as per the clinicians discretion.

IOP at 12 months will be the primary outcome measure. The target pressure will be based on the Asia Pacific Glaucoma Guidelines. For PAC with high IOP and PAS and early PACG, the target will be $>/=20\%$ from base line or 18mmHg whichever is lower. b. The Asia Pacific Glaucoma Guidelines classifies “PAC with High IOP and PAS” to be “glaucoma with moderate 5-year risk for visual loss” and to treat the IOP with a target of $>/=20\%$ or 18mmHg whichever is lower.

The target IOP is 18mmHg for patients with PAC or mild PACG. If the IOP rises above 18mmHg in 2 consecutive visits then the original glaucoma medication(s) will be reinstated or as per the clinicians discretion.

The patient will be masked to the treatment arm given, but the investigators will not be masked.

The procedure will be performed by 2 surgeons: [name] and [name], the follow up visits and monitoring of pressure will be done by the investigation team.

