2.2. Primary Objectives

To assess the efficacy of the iStent trabecular micro-bypass stent (Glaukos Corporation, Laguna Hills, CA) in combination with cataract surgery in subjects with primary angle closure and mild to moderate primary angle closure glaucoma

2.3. Potential Risks and benefits:

a. End Points – Efficacy

The primary outcome is: unmedicated IOP \leq 21mmHg at 1 year and mean IOP at 1 year.

A secondary outcome measure is medication reduction at 1 year post operation

b. End Points - Safety

Safety measures include best corrected visual acuity, slit lamp observations, complications and adverse events

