5.1. Summary of Study Design

Briefly describe the study design and indicate, in general terms, how the design will fulfil the intent of the study.

Single centre, randomised prospective trial, the patient and the IOP checking staff will be blinded. Randomised by random envelope shuffle technique.

2 arms: phacoemulsification alone and phacoemulsification and iStent.

16 patients in each arm, 32 patients in total.

The equal allocation 1:1 ratio will help determine which arm is more efficacious. The regular follow up will determine the safety of the iStent device. The randomisation will avoid surgical bias. The blinding of the patient and IOP measuring staff will avoid observational bias.

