11.2. Statistical and Analytical Plans

a. General Considerations

Independent t- tests will be used to compare both groups at 12 months post operation

“Success” will be defined as IOP unmedicated IOP</=21mmHg at 1 year and unmedicated IOP reduction of >/=20% at 1 year, with no additional anti-glaucomatous medications at 1 year. The rational for 20% reduction is based on published RCT trials that use 20% as a standard reduction expected from this device. The same reduction percentage is used for comparison to other published data.

Chi-square test will be used to compare success versus failure in both groups.

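### An open discretion clause in the 18 mmHg restart rule, in a trial with unmasked investigators, leaves the responder and medication outcomes open to arm-dependent prescribing

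*Protocol*

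**What the plan says.** **Restart rule.** Protocol section 5 gives the rule twice in the same words: "If the IOP rises above 18mmHg in 2 consecutive visits then the original glaucoma medication(s) will be reinstated or as per the clinicians discretion". The default is therefore numeric, and discretion is a stated alternative to it. The protocol does not say whether or when a restored drop may be stopped, and section 8.6 (Concomitant therapy) is marked not applicable.

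**Masking.** Section 5: "The patient will be masked to the treatment arm given, but the investigators will not be masked". It adds that "the follow up visits and monitoring of pressure will be done by the investigation team". Sections 6.1 and 8.5 mask the patient and the two people who take and read the pressure. Section 5.1 concludes: "The blinding of the patient and IOP measuring staff will avoid observational bias". Section 5 also declares that post-operative care does not differ between the arms.

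**Outcomes that depend on drops.** Section 2.3: "The primary outcome is: unmedicated IOP" at or below 21 mmHg at 1 year, listed together with mean IOP. Then: "A secondary outcome measure is medication reduction at 1 year post operation". In section 11.2, a successful result "will be defined as IOP unmedicated IOP</=21mmHg at 1 year and unmedicated IOP reduction of >/=20% at 1 year". The same definition adds a condition on treatment: "with no additional anti-glaucomatous medications at 1 year". Success is compared by a chi-square test. Under section 3.3 every patient enters on at least one drop.

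**The concern.** Drop status at 1 year is part of what is scored. Two eyes with identical masked readings, both above 18 mmHg at two consecutive visits, can be treated differently under section 5 without breaching its wording: one restarted under the default, the other left alone at the clinician's discretion. If that choice leans by arm, the responder comparison and the medication comparison carry the lean as if it were a treatment effect. Masked tonometry does not prevent this, because the tonometrist does not prescribe. The claim in section 5.1 covers the measurement only.

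The responder outcome is listed as primary in section 2.3, and with 16 eyes per arm a few prescribing decisions can matter.

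**Working it through.** **The plan's own figure.** The protocol gives no number on this point. Its sample size concerns mean IOP and reproduces from the section 11.1 inputs: 2 × (1.960 + 0.842)² × 2.4² / 2.6² = 13.4, so 14 per arm. Nothing below bears on it.

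**Step 1: the route from prescribing to outcome.**
- Restarted and still on drops at month 12: the eye has no unmedicated pressure to score, so it cannot readily be a success under 2.3 or 11.2.
- Left off drops: the eye must still meet the IOP limits, read by masked staff. Discretion alone cannot make it a success.
- Number of drops at 1 year: this is the prescriber's decision in both directions.

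**Step 2: how many eyes lie between the two thresholds.** The restart trigger is above 18 mmHg and the responder limit in 2.3 is 21 mmHg. Inputs are the 1-year values in section 11.1: control 19.2 (SD 3.1), combined 16.6 (SD 3.5). Assumptions not in the protocol: these are off-drop pressures, and they are normally distributed.

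P(18 < IOP ≤ 21) = Φ((21 − m)/s) − Φ((18 − m)/s)
- Control: Φ(0.581) − Φ(−0.387) = 0.719 − 0.349 = 0.370, and 16 × 0.370 = 5.9 eyes.
- Combined: Φ(1.257) − Φ(0.400) = 0.896 − 0.655 = 0.240, and 16 × 0.240 = 3.8 eyes.

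This is the spread at one visit, whereas the trigger needs two consecutive visits, so it indicates the size of the zone rather than counting triggered eyes. Section 11.2 also requires a 20% fall, so its limit is the lower of 21 and 0.8 × baseline. The full band applies there only for baselines of at least 21/0.8 = 26.25 mmHg. With an assumed baseline of 24 mmHg the limit is 19.2, and the band is 0.500 − 0.349 = 0.151 in control and 0.771 − 0.655 = 0.116 in the combined arm.

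**Step 3: how sensitive the test is.** With 5/16 against 11/16 successes, the uncorrected chi-square is 32 × 96² / 16⁴ = 4.50, p = 0.034. With 5/16 against 10/16 it is 3.14, p = 0.077. So one eye can move the result across 0.05. With continuity correction, 5 against 11 gives 32 × (96 − 16)² / 16⁴ = 3.125, p = 0.077, and this particular example is no longer significant. Section 11.2 does not say which version is meant.

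**Step 4: illustration of a lean.** Assume no stent effect, the same true success rate (50% to 70%) in both arms, and restarts that turn some control successes into failures in that arm only. Exact binomial enumeration at 16 per arm, nominal 5%:

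| Control successes lost (of 16) | Rejection rate, uncorrected | Rejection rate, corrected |
|---|---|---|
| 0 | 5–6% | about 2% |
| 2 | 11–12% | about 5% |
| 3 | 19–20% | about 10% |
| 4 | 30–32% | about 18% |

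The number lost is an assumption; the protocol gives no basis for any row.

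**The case against.** The best defence has five parts.

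- *There is a numeric rule, and section 5 says both arms are managed alike.* Both are true. A reader might infer that all drop decisions are left to discretion; the protocol does not say so. Restarting has a default, and on stopping drops the text is silent rather than permissive. What remains is that the equal-management statement has no mechanism behind it, and the one rule that could supply it contains the opt-out.
- *The prescriber is not named as unmasked.* Correct. That the deciding clinician knows the arm is an inference from unmasked investigators and follow-up by the investigation team. It is the natural reading, since only the patient and the IOP staff are masked.
- *Success still requires masked IOP limits.* This stands and limits the point: a restart can remove a success, but withholding drops cannot create one by itself.
- *Scoring of restored drops is not spelled out.* This also stands. Section 11.2 excludes additional drops, and restored original drops are arguably not additional. But it also requires an unmedicated pressure, and no drop-free period is described, so scoring such an eye as a success would be hard to justify.
- *Mean IOP is the sized comparison and section 5 names IOP at 12 months as primary.* The point does not extend to mean IOP. There the counterweight runs the other way: keeping stent eyes off drops would tend to raise that arm's mean. The responder outcome is nevertheless also listed as primary in 2.3.

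It is not a matter for an analysis plan. Who decides on drops, and whether that person knows the arm, is trial conduct and cannot be repaired at analysis.

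**Conclusion.** The point holds in limited form. Section 5 sets a default restart rule, allows it to be replaced by clinician judgement, and does not mask the investigators. Two outcomes, unmedicated success and medication reduction, are therefore open to arm-dependent prescribing that masked tonometry does not prevent. The zone between the restart trigger and the 21 mmHg limit is not small: about 37% of control and 24% of combined-arm eyes, assuming normal, off-drop 1-year values. It is smaller under the 20% criterion when baseline is below 26.25 mmHg.

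A reader might go further and conclude that the trial is biased towards the stent, or attach a specific inflated type I error to it. The protocol supports neither. It gives no evidence that prescribing will differ by arm or in which direction, and the rates above depend on an assumed asymmetry and on whether the chi-square is continuity-corrected. This is a cheap improvement worth making, not a fatal flaw.

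**What to change.** In section 5:

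1. Delete the discretion clause in both places and make the 18 mmHg rule binding in both arms up to month 12, applied to the masked two-person readings.
2. Have any departure (withholding, or stopping a restored drop) decided by an existing non-operating team member who is not told the arm, with the reason recorded.
3. Let the treating clinician override for safety only. Because that clinician may know the arm, record overrides, report them by arm, and add a sensitivity analysis that scores those eyes by what the rule required.

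As clarifications only: state in 2.3 and 11.2 how an eye on restored drops at month 12 is scored, and limit the sentence in 5.1 to the pressure reading.

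**Cost.** Some loss of prescribing freedom and a small masking and logging task: at most 7 visits × 32 patients = 224 readings to check against the rule. A binding rule also means that eyes settling between 18 and 21 mmHg will usually go back on drops and not count as successes, but equally in both arms. There is no extra visit, no washout, no added staff and no change to the 18 mmHg target.

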5.1. Summary of Study Design

Briefly describe the study design and indicate, in general terms, how the design will fulfil the intent of the study.

Single centre, randomised prospective trial, the patient and the IOP checking staff will be blinded. Randomised by random envelope shuffle technique.

2 arms: phacoemulsification alone and phacoemulsification and iStent.

16 patients in each arm, 32 patients in total.

The equal allocation 1:1 ratio will help determine which arm is more efficacious. The regular follow up will determine the safety of the iStent device. The randomisation will avoid surgical bias. The blinding of the patient and IOP measuring staff will avoid observational bias.

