6.1. Randomisation and Blinding

This section should describe randomisation and blinding procedures (if applicable to the

study design). Include a description or a table that describes how study subjects will be assigned to the study groups. The timing and procedures for planned and unplanned breaking of randomization codes should be included. Include statement when unmasking may occur and who may unmask.

Randomised controlled study. 1:1 ratio allocation 32 patients 16 phacoemulsification alone 16 phacoemulsification with iStent Randomisation by shuffled envelope system.

Follow up will be at 1 day, 1 week, 1 month, 3 months, 6 months, 1 year after surgery.

Patient will be blinded to the procedure.

The IOP measure and reader will be blinded to the procedure.

There will be no planned breaking of randomisation.

Unplanned breaking will happen if any envelopes are damaged or lost.

Unmasking will take place after 1 year post operation by the study team to inform the patient of the procedure.

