11. SAMPLE SIZE AND STATISTICAL METHODS

11.1. Determination of Sample Size

Details on sample size calculation and the means by which data will be analysed and interpreted.

In particular, specify all of the following:

- Null Hypothesis
Phacoemulsification with micro-bypass stent has no difference in effect on IOP compared to phacoemulsification alone in primary angle closure and primary angle closure glaucoma at 1 year after surgery.
- Alternate hypothesis
Phacoemulsification with micro-bypass stent has a better IOP lowering effect compared to phacoemulsification alone in primary angle closure and primary angle closure glaucoma at 1 year after surgery.
- Type I error rate = 0.05
- Type II error rate = 0.2

Sample Size Calculation:

Based on published data of phaco and phaco iStent RCT in open angle glaucoma:

Mean IOP for control at 1 year (phaco only group) – 19.2mmHg +/- 3.1

Mean IOP for combined group at 1 year (phaco+istent group) – 16.6mmHg +/-3.5

Alpha = 0.05

Power = 0.80

SD: 2.4

Difference: 2.6

Sample size = 14 in each arm

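### Two surgeons operate, but the allocation is not balanced by surgeon and nothing says the surgeon is settled before the envelope is opened: a cheap, minor gain in balance and precision is left unused

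*Protocol*

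**What the plan says.** Section 5 of the protocol states that "The procedure will be performed by 2 surgeons" and sets "1:1 ratio allocation", with "16 patients in each arm, 32 patients in total". The method of allocation is given in section 6.1 as "Randomisation by shuffled envelope system"; sections 4, 5, 5.1 and 6.3 say the same in similar words. None of them mentions stratification or separate sequences by surgeon. None says how patients come to one surgeon or the other, or whether that is decided before allocation is known. Section 5 also says that the investigators are not masked.

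Section 5.1 says of the design that "The randomisation will avoid surgical bias" and does not define the term. The next sentence credits masking with protecting the measurement of IOP. Section 11.2 names an independent t-test for the 12-month comparison, with no surgeon term.

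**The concern.** A single shuffle can fix 16 patients per arm overall, but it leaves each surgeon's own split between stent and control to chance. If the two surgeons' patients differ in 12-month IOP, an uneven split carries part of that difference into the arm contrast, and the planned t-test does not remove it. The protocol gives some reason to expect operator differences: the stent has not been studied in angle closure (1.2), this is the first trial of the device in Singapore (section 1.2, under the rationale for the study purpose), and failed insertion is a listed ground for withdrawal (3.5).

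The timing matters for a second reason. If the choice of surgeon could follow the opening of the envelope, the surgeon mix could differ systematically between arms, and randomisation would not protect against that.

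A surgeon term might appear in a SAP that is not at hand. The allocation scheme cannot wait for one, because it has to be fixed before the first patient is randomised.

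**Working it through.** **Inputs from the protocol.** 32 patients, 16 per arm, two surgeons (section 5). From 11.1: "Type I error rate = 0.05", power 0.80, SD 2.4 mmHg, "Difference: 2.6" (mmHg), "Sample size = 14 in each arm".

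**Assumptions, because the protocol is silent.** The division of cases between surgeons is varied from 8:24 to 16:16. The gap *g* between surgeons in mean 12-month IOP is 1, 2 or 3 mmHg and the same in both arms. The surgeon is settled independently of allocation. Tests are two-sided.

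**1. The plan's own figure.** n per arm = 2 × (1.96 + 0.84)² × 2.4² / 2.6² = 13.4, so 14. The stated figure reproduces (the exact t calculation gives 15).

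**2. Chance of imbalance.** With 16 of 32 envelopes marked stent, the number of stent cases among one surgeon's *m* patients is hypergeometric.

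| Cases per surgeon | Arms differ by ≥4 of one surgeon's cases | by ≥6 |
|---|---|---|
| 16:16 | 28.9% (10:6 or worse) | 7.6% (11:5 or worse) |
| 20:12 | 27.3% | 6.6% |
| 24:8 | 22.0% | 3.7% |

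**3. Effect on the contrast.** If one surgeon has *a* stent and *b* control cases, the shift is *g* × (*a* − *b*)/16. For 10:6 this is *g* × 4/16 = 0.25*g*, that is 0.25, 0.50 and 0.75 mmHg, or 10%, 19% and 29% of 2.6 mmHg.

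**4. Bias, error rate and precision over all randomisations.** The mean of *a* − *b* is zero for a 16:16 division, so the expected shift is zero. In 100,000 simulated trials per gap, the type I error of the unadjusted t-test was 0.050, 0.051 and 0.050. Among trials with a difference of 4 or more cases it was about 0.06, 0.08 and 0.10. Under balance the standard error is 2.4 × √(2/16) = 0.849 mmHg. The SD of (*a* − *b*)/16 is 0.180, so without stratification the SD of the estimate is √(0.849² + (0.180*g*)²) = 0.87, 0.92 and 1.01 mmHg.

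**5. Power at 16 per arm, effect 2.6, SD 2.4, 16 cases per surgeon.**

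| Gap (mmHg) | Single shuffle, t-test | Within surgeon, t-test | Within surgeon, surgeon term |
|---|---|---|---|
| 1 | 0.83 | 0.83 | 0.84 |
| 2 | 0.78 | 0.80 | 0.84 |
| 3 | 0.71 | 0.73 | 0.84 |

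The last column is a noncentral t with noncentrality 2.6/0.849 = 3.06 and 29 degrees of freedom, and does not depend on the gap. Stratifying without the surgeon term makes the t-test conservative (type I error 0.046, 0.034 and 0.020), so the two changes belong together.

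**6. Surgeon term without stratification.** The noncentrality is multiplied by √(1 − *r*²), where *r* = (*a* − *b*)/16. At 10:6 that is 3.06 × √(1 − 0.0625) = 2.97. Averaged over the hypergeometric splits, power is about 0.83 at any gap. Most of the loss can therefore be recovered in the analysis alone.

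**The case against.** The strongest reply is that randomisation does what section 5.1 claims. The natural meaning of the phrase there is that the surgeon cannot choose which operation a patient receives, and on that meaning the sentence is correct. A reader might infer that the sentence is false because the arms may be unbalanced by surgeon. The documents do not support this: nothing in 5.1 promises balance by operator, and chance imbalance with zero expectation and a 5% error rate is not bias. A reader might also infer that a surgeon effect could not be separated from a stent effect. That is wrong as well, because a 10:6 split is partial imbalance and a surgeon term separates the two.

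The size also rests on an assumed gap that nothing in the protocol supports with a figure. The protocol's own reasons for operator differences concern stent insertion. If the gap existed only in stent cases, a 10:6 split at 2 mmHg would move the contrast from its balanced value by (10/16 − 8/16) × 2 = 0.25 mmHg, half of the 0.50 above. The protocol does not say that the surgeon is known when a patient is listed, and the absence of stratification is read from silence. Shorter sequences are also easier for unmasked surgeons to guess.

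All of this stands, and it makes the point a minor one. It does not answer the silence on when the surgeon is settled, nor the fact that better balance and precision are available at almost no cost.

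**Conclusion.** The point holds as a minor improvement to design and analysis. No error in the stated sample size and no invalid test is shown. Under independent assignment of surgeons there is a 22% to 29% chance that one surgeon's cases differ by 4 or more between the arms. The resulting shift is 0.25 to 0.75 mmHg for assumed gaps of 1 to 3 mmHg, and the unadjusted test gives up about 0.01 to 0.13 of power against allocation within surgeon plus a surgeon term. If the gap is zero, almost nothing is lost or gained.

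The power figures use the planned SD of 2.4 mmHg and an equal division of cases. Section 11.1 also quotes larger arm SDs (3.1 and 3.5); with those, power would be lower throughout and the surgeon gap would matter relatively less.

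The zero expected shift depends on the surgeon being settled independently of allocation. The protocol does not say so. It does not say the contrary either, so real bias by this route is a possibility to close off and not something the documents show.

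**What to change.** **Before recruitment.** In sections 5 and 6.1, state that the operating surgeon is settled and recorded before the envelope is opened. Allocate 1:1 within surgeon, from a separate sequence for each, with sequences and block sizes kept from the surgeons. In 11.2, include surgeon as a factor in the 12-month IOP comparison.

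**If recruitment has begun.** Leave the allocation as it is, add only the surgeon term, and report the surgeon-by-arm table.

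**In 5.1.** Reword the sentence to say that randomisation prevents the surgeon from choosing the operation.

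**Cost.** Two envelope sequences in place of one, one degree of freedom (29 in place of 30), and somewhat easier guessing of the shorter sequences by unmasked surgeons, which varying block sizes limit. An unfinished last block may leave the overall split slightly off 16:16. The required sample size does not change.
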